4.1. Vaccine/Stratum Misallocation

- Randomized into the wrong MenACWY stratum: These participants will be included in the safety population for the safety analysis and will be reported under the MenACWY stratum according to true MenACWY history. These participants will also be included in the mITT population for immunogenicity analyses if data are available, and will be reported under the MenACWY stratum according to their true MenACWY history (MenACWY experience recorded on the CRF for prior MenACWY history). However, these participants will be excluded from the analyses using evaluable immunogenicity population(s) for the MenACWY endpoints, but included in the analyses using evaluable immunogenicity population(s) for the MenB endpoints. A participant's true MenACWY history (naïve/experienced) will be ascertained programmatically from the prior meningococcal vaccine data set in the clinical database before the planned unblinding. Serogroups contained within the prior meningococcal vaccine received will be determined by the sponsor's global medical monitor.
- Participants randomized to the safety subset but for whom immunogenicity data are collected according to the CRF: These participants will be reported according to their true immunogenicity subset per the CRF. A participant's true immunogenicity/safety assignment will be ascertained programmatically in the clinical database before the planned unblinding. These participants will be included in the safety population and the mITT population. For the evaluable populations, they will be excluded.

- Vaccinated but not randomized: These participants will be included in the safety population for safety analysis and will be reported under the vaccine group based on the vaccine received, but will be excluded from immunogenicity analyses.
- Randomized but not vaccinated: These participants will be included in the ITT population and excluded from any safety analyses. They may be included in the mITT population if any assay results are available and will be reported under their randomized group for immunogenicity analyses.
- Randomized but received incorrect vaccine: These participants will be included in the mITT population for immunogenicity analyses if data are available and will be reported under the vaccine group based on the randomized vaccine. These participants will also be included in the safety population for safety analysis and will be reported under the vaccine group based on the vaccine received.

5. GENERAL METHODOLOGY AND CONVENTIONS

5.1. Hypotheses and Decision Rules

The primary immunogenicity objectives are:

- To demonstrate that the immune response for MenA, MenC, MenW, and MenY induced by 2 doses of MenABCWY is noninferior to the immune response induced by 1 dose of MenACWY-CRM, for ACWY-naïve and ACWY-experienced participants separately.
- To demonstrate that the immune response for MenB induced by 2 doses of MenABCWY is noninferior to the immune response induced by 2 doses of Trumenba.

The primary objectives of noninferiority will be met if:

- The lower limit of the 2-sided 95% CI for the difference in seroresponders (Group 1 - Group 2) is $> -10\%$ for all of the MenACWY test strains at 1 month after the second vaccination for Group 1 and at 1 month after the first vaccination for Group 2; and
- The lower limit of the 2-sided 95% CI for the difference in seroresponders (Group 3 - Group 4) is $> -10\%$ for all of the MenACWY test strains at 1 month after the second vaccination for Group 3 and at 1 month after the first vaccination for Group 4; and
- The lower limit of the 2-sided 95% CI for the differences in 4-fold rises and composite responses (Groups 1+3 - Groups 2+4) is $> -10\%$ for all of the primary MenB test strains at 1 month after the second vaccination.

For the MenACWY noninferiority evaluation in ACWY-naïve participants, the immune response will be evaluated at 1 month following Vaccination 2 for Group 1 and at 1 month following Vaccination 1 for Group 2. The null hypothesis (H_0) for each MenACWY serogroup for noninferiority is as follows:

$$H_0: \pi_{G1} - \pi_{G2} \leq -10\%$$

where π_{G1} and π_{G2} are the percentages of participants who achieve a 4-fold rise in hSBA titers for MenA, MenC, MenW, and MenY.

π_{G1} and π_{G2} represent Group 1 and Group 2 participants, respectively.

For the MenACWY noninferiority evaluation in ACWY-experienced participants, the immune response will be evaluated at 1 month following Vaccination 2 for Group 3 and at 1 month following Vaccination 1 for Group 4 participants.

The null hypothesis (H_0) for each MenACWY serogroup for noninferiority is as follows:

$$H_0: \pi_{G3} - \pi_{G4} \leq -10\%$$

where π_{G3} and π_{G4} are the percentages of participants who achieve a 4-fold rise in hSBA titers for MenA, MenC, MenW, and MenY.

π_{G3} and π_{G4} represent Group 3 and Group 4 participants, respectively.

The null hypothesis (H_0) for noninferiority for each primary MenB test strain is as follows:

$$H_0: \pi_{G1+G3} - \pi_{G2+G4} \leq -10\%$$

where π_{G1+G3} and π_{G2+G4} are the percentages of 4-fold rises and composite responses for Groups 1 and 3 combined and for Groups 2 and 4 combined, respectively, at 1 month after the second vaccination.

The primary hypotheses for MenACWY endpoints and the primary hypotheses for MenB endpoints will be tested simultaneously. The primary objectives of noninferiority will be met only if all statistical criteria for the objectives were met. Therefore, the multiplicity of primary objectives does not require an alpha adjustment.

The secondary objective with hypothesis testing is:

- To demonstrate that the immune response induced by 1 dose of MenABCWY is noninferior to the immune response induced by 1 dose of MenACWY-CRM, for ACWY-naïve and ACWY-experienced participants separately.

Hypothesis testing for the secondary objective will be performed only if the primary objectives are successful.

The secondary objective of noninferiority will be met if:

- The lower limit of the 2-sided 95% CI for the difference in seroresponders (Group 1 - Group 2) is $> -10\%$ for all of the MenACWY test strains (at 1 month after the first vaccination for Group 1 and at 1 month after the first vaccination for Group 2); and
- The lower limit of the 2-sided 95% CI for the difference in seroresponders (Group 3 - Group 4) is $> -10\%$ for all of the MenACWY test strains (at 1 month after the first vaccination for Group 3 and at 1 month after the first vaccination for Group 4).

5.2. General Methods

Descriptive summary statistics will be provided for all endpoints. Unless otherwise explicitly stated, descriptive statistics for continuous variables are n, mean, median, standard deviation, minimum, and maximum. Descriptive statistics for categorical variables are the proportion (%) and the n (the numerator) and N (the denominator) used in the calculation of the proportion.

5.2.1. Analyses for Binary Endpoints

The number and percentage of participants in each category will be summarized. The 95% CI for percentages, and for difference in percentages, will also be presented, where appropriate. The 95% CI for the proportion will be constructed by the Clopper-Pearson method described by Agresti.¹ The 95% CI will be presented in terms of percentages.

For both Tier 1 and Tier 2 events, the 95% CIs for the difference in percentage of participants reporting the events between MenABCWY and Trumenba combined groups will be calculated using the Miettinen and Nurminen method.² There are no Tier 1 events identified for MenABCWY at this stage.

5.2.1.1. Immunogenicity Data

Each MenB strain has a validated LLOQ value defined (Table 13). Each MenACWY serogroup has a qualified LLOQ value defined (Table 14).

Table 13. Validated hSBA LOD and LLOQ for MenB Primary Strains

Strain Type	Strain Variant	LOD	LLOQ
Primary	A22	1:4	1:16
	A56	1:4	1:8
	B24	1:4	1:8
	B44	1:4	1:8

Abbreviations: hSBA = serum bactericidal assay using human complement; LLOQ = lower limit of quantitation; LOD = limit of detection; MenB = *Neisseria meningitidis* group B.

Table 14. Validated hSBA LOD and LLOQ for MenACWY Serogroups

Serogroup	LOD	LLOQ
MenA	1:4	1:8
MenC	1:4	1:8
MenW	1:4	1:8
MenY	1:4	1:8

Abbreviations: hSBA = serum bactericidal assay using human complement; LLOQ = lower limit of quantitation; LOD = limit of detection; MenACWY = *Neisseria meningitidis* group A, C, W, and Y.

For the immunogenicity subset, all hSBA titers assessed for either MenB or MenACWY will be analyzed as below:

At each visit where assay titers are available (Visits 1, 2, and 4), participants with hSBA titers \geq LLOQ will be derived as follows:

- = ●, if the assay result is missing, indeterminate, or otherwise unavailable;
- = 1, if the assay result meets the specific LLOQ value;
- = 0, if the assay result does not meet the specific LLOQ value.

Similarly, for all hSBA titers assessed, binary variables of assay results at each visit at which assay titers are analyzed and that achieve specific thresholds will be derived as follows:

- = ●, if the assay result is missing, indeterminate, or otherwise unavailable;
- = 1, if the assay result meets the specific threshold value;
- = 0, if the assay result does not meet the specific threshold value.

The threshold values for MenB and MenACWY titers are:

- $\geq 1:4, \geq 1:8, \geq 1:16, \geq 1:32, \geq 1:64, \text{ and } \geq 1:128$ for MenB hSBA titers
- $\geq 1:8, \geq 1:16, \geq 1:32, \geq 1:64, \text{ and } \geq 1:128$ for MenACWY hSBA titers

A composite response will be computed at 1 month after Vaccination 2. The composite response is defined as participants who have assay results that are \geq LLOQ for all 4 of the primary MenB strains at the same visit.

- = ●, if the assay result is missing, indeterminate, or otherwise unavailable for at least 1 of the 4 MenB primary strains;
- = 1, if all 4 MenB primary strains have assay results \geq LLOQ at the same visit;
- = 0, if not all 4 MenB primary strains have assay results \geq LLOQ.

The 4-fold response in assay titers from baseline (Visit 1, prevaccination) to 1 month after Vaccinations 1 and 2 (Visits 2 and 4) will be defined as follows:

- For participants with a baseline hSBA titer below the LOD (or an hSBA titer of $<1:4$), a 4-fold response is defined as an hSBA titer of $\geq 1:16$.
- For participants with a baseline hSBA titer of \geq LOD (ie, hSBA titer of $\geq 1:4$) and $<$ LLOQ, a 4-fold response is defined as an hSBA titer of ≥ 4 times LLOQ.
- For participants with a baseline hSBA titer of \geq LLOQ, a 4-fold response is defined as an hSBA titer of ≥ 4 times the baseline titer.

The 4-fold response variable for the MenB and MenACWY strains will be computed as:

- = ●, if the assay result at baseline or the specific time point is missing, indeterminate, or otherwise unavailable;
- = 1, if the assay result meets 1 of the 3 definitions for a 4-fold response;
- = 0, if the assay result does not meet 1 of the 3 definitions for a 4-fold response.

5.2.1.2. Safety Data

All safety endpoints (including reactogenicity data recorded from the e-diary and AE data recorded from the CRF) will be summarized with percentages and 95% exact CIs (Clopper-Pearson method) for each group.

For both Tier 1 and Tier 2 events (AEs by PTs during the vaccination period), the 95% CIs for the difference in percentage of participants reporting the events between MenABCWY and Trumenba combined groups will be calculated using the Miettinen and Nurminen method.

The CIs presented for the safety data will not be used to test hypotheses but will be used to determine which events may need further clinical investigation. No adjustment for multiplicity is needed. There are no Tier 1 events identified for MenABCWY.

5.2.2. Analyses for Continuous Endpoints

5.2.2.1. Geometric Mean Titers

GMTs will be computed for each hSBA titer for the MenB and MenACWY strains. If the hSBA result is below LLOQ, it will be set to $\frac{1}{2}$ the LLOQ for the GMT calculation. The assay results at each blood sampling time point will be (natural-log) logarithmically transformed for analysis. GMTs are obtained by log transformations of indicated values, averaging the log values, then exponentiating the result. The associated 2-sided 95% CIs are obtained by exponentiating the limits of CIs for the mean logarithm of the hSBA titers (based on the Student t distribution).

5.2.2.2. Reverse Cumulative Distribution Curves

RCDCs for MenB and MenACWY strains for a combination of available time points and vaccine groups may be generated.

5.2.2.3. Days Missed

Days in which a participant missed school and/or work will be captured on the AE checklist. The data captured at each visit will be summarized and the total number of missed days of school and/or work will be obtained.

5.3. Methods to Manage Missing Data

5.3.1. Safety Data

Standard algorithms on handling missing AE dates will be applied according to Pfizer safety rules.

5.3.1.1. Reactogenicity Data

For derived variables based on reactogenicity data, if any day of the 7-day e-diary is available, the “any day (Days 1-7)” data will be considered nonmissing. Participants are excluded from the analysis if they do not receive the particular dose or the safety data are missing on all days within the interval.

The reactogenicity data are collected through the e-diary, which does not allow participants to skip the question. Therefore, for a specific day, as long as the e-diary data are transferred for that day, all of the reactogenicity data for the participant on that day are nonmissing. The e-diary transmission and completion status will be summarized per [Section 6.5.4](#). The e-diary completion summary will provide the missing data information on the reactogenicity data.

Based on data from available studies, the missing data on reactogenicity are minimal, which is consistent with Li et al (2011).³ No sensitivity analysis is planned for reactogenicity data.

5.3.2. Immunogenicity Data

As assay data are expected to be missing completely at random, the primary analysis for the primary objectives will be based upon the observed, determinate observations. No imputation will be performed. The proportion of participants with missing immunogenicity data may be summarized at each blood sampling visit for each MenB and MenACWY strain. The denominator will be the as-randomized population. The category of missing reasons (QNS, indeterminate, not done, dropout) may also be summarized.

If 10% or more of the participants in any group have missing hSBA data for the MenB or MenACWY strains for non-withdrawal-related reasons, a sensitivity analysis using an MMRM in the immunogenicity subset may be applied for each strain (GMT). For the MenACWY strains, the ACWY-naïve and ACWY-experienced participants will be analyzed separately. For the primary MenB strains, Groups 1 and 3 combined will be described against Groups 2 and 4 combined.

The MMRM uses maximum likelihood estimation and it is under the assumption that the missingness is at random (MAR). To account for the intraparticipant correlation among the repeated measures, an unstructured covariance matrix will be used. In case the model does not converge, further covariance structures will be explored (ie, first-order autoregressive, compound symmetry). Independent variables (race, sex, etc) may be dropped from the model because of nonconvergence.

$\text{Log (hSBA)} = \text{randomized group(s)} + \text{race} + \text{sex} + \text{geographic location (US; ex-US)} + \text{age at randomization} + \text{visit}$. The intercept will be set as random effect.

In addition to type III analysis output, least-squares GMTs at each visit will be summarized for each strain.

These analyses will use the mITT population, using $\frac{1}{2}$ LLOQ to set the hSBA values below LLOQ.

Similar to GMT, a GLIMMIX will be used. The response variables are binary variables (composite response and 4-fold response), and a logit link will be used. The model will be similar to above. As the 4-fold responses will not have a response at Visit 1, the GLIMMIX will use baseline hSBA titer as covariate and blood sampling time points at Visits 2 and 4 as repeated dependent variables. The composite response analyses will be similar to the GMT analyses, with composite responses at all 3 visits modeled as dependent variables. This analysis will only be applied to the mITT population. The model-estimated response rates and the 95% CIs will be summarized. The groups for the ACWY-naïve and ACWY-experienced participants will be similar to the GMT analysis.

For the hSBA assay results, the following values will be set to missing: QNS (insufficient sera), indeterminate results, and not done. Participants without blood draw (ie, dropout) will also have missing data for immunogenicity.

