2.2.2.3. Pentavalent Meningococcal Vaccine (MenABCWY)

MenABCWY is an investigational pentavalent meningococcal vaccine consisting of bivalent rLP2086 (supplied as a 0.7-mL PFS) and MenACWY-TT, which are administered as a single injection after reconstituting the MenACWY-TT components with the bivalent rLP2086 suspension. MenABCWY has been administered to 543 individuals participating in Study B1971057.

Results from B1971057 demonstrated the immunogenicity and safety of MenABCWY in adolescents and young adults. This was a randomized, active-controlled, observer-blinded multicenter trial in which approximately 1600 participants \geq 10 to $<$ 26 years of age were randomly assigned to receive either MenABCWY (n=543) on a 0-month and 6-month schedule, or Trumenba on a 0-month and 6-month schedule and MenACWY-CRM (n=1057) at the same time as the first dose of Trumenba. All participants were naïve to any meningococcal group B vaccine prior to enrollment and approximately half were naïve to prior MenACWY vaccination, while the other half were considered ACWY-experienced, having had no more than 1 previous ACWY component vaccine at least 4 years prior to enrollment. Stage 1, which included the vaccination phase of the primary series, is now complete.

Immunogenicity noninferiority evaluations of hSBA responses to the MenACWY component of MenABCWY showed that MenABCWY, both after 1 and 2 doses, was noninferior to a single dose of MenACWY-CRM by 3 different statistical methods for individuals who were either ACWY-naïve or ACWY-experienced. One and 2 doses of MenABCWY were noninferior to 1 dose of MenACWY-CRM at the 10% margin. Specifically, for ACWY-naïve participants, the percentage-of-responder (≥ 4 -fold rise) differences between a single dose of MenABCWY compared to a single dose of MenACWY-CRM were 1.1% (-2.1, 3.7) for serogroup A, 5.5% (-1.3, 11.9) for serogroup C, 10.7% (4.9, 16.1) for serogroup W, and 14.1% (8.1, 19.7) for serogroup Y. Among ACWY-experienced participants, the percentage differences were -0.8% (-4.5, 2.1) for serogroup A, -2.4% (-6.4, 0.9) for C, -0.8% (-4.5, 2.0) for W, and -0.3% (-4.6, 3.3) for Y. Similarly, noninferiority was also established for ≥ 4 -fold rise in the percentage of responders after 2 doses of MenABCWY compared to a single dose of MenACWY-CRM for ACWY-naïve and ACWY-experienced participants.

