6.1.1.1.1. Main Analysis

- Estimand strategy: Hypothetical.
- Analysis set: ACWY-naïve participants: Post-Vaccination 1 evaluable population for Group 2 and post-Vaccination 2 evaluable population for Group 1.
- Analysis methodology: 95% CI for the difference in the percentage of seroresponders (defined as participants achieving a 4-fold rise from baseline for each MenACWY test strain) calculated by the Miettinen and Nurminen procedure.
- Intercurrent events and missing data: Missing serology results will not be imputed. Participants will be summarized according to the vaccine group to which they were randomized.
- The 95% CIs for the difference in the percentage of seroresponders, defined as participants achieving a 4-fold rise from baseline for each MenACWY test strain, 1 month after Vaccination 2 in Group 1 compared to 1 month after Vaccination 1 in Group 2 will be calculated using the Miettinen and Nurminen method. The lower limit of the CI will be used in the hypothesis test for noninferiority as detailed in [Section 5.1](#). Exact 2-sided 95% CIs for the percentages of seroresponders will be provided using the Clopper-Pearson method.

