6.3.1.1.3. Main Analysis

- Estimand strategy: Hypothetical.
- Analysis set: mITT population for Groups 2 and 4.
- Analysis methodology: Descriptive summary statistics for MenACWY strains for participants who received at least 1 dose (Groups 2 and 4) of MenACWY-CRM.
- Intercurrent events and missing data: Participants will be summarized according to the vaccine group to which they were randomized. Missing serology data will not be imputed.

For each group (ACWY-naïve and ACWY-experienced participants separately) in the analysis set, the following analysis will be described:

- The percentage of participants achieving an hSBA titer $\geq 1:8$ for each MenACWY test strain, at baseline and 7 months after Vaccination 1 in Groups 2 and 4.
- hSBA GMTs for each of the MenACWY test strains, at baseline and 7 months after Vaccination 1 in Groups 2 and 4.
- The percentage of participants achieving at least a 4-fold rise in hSBA titers for each of the MenACWY test strains, at baseline and 7 months after Vaccination 1 in Groups 2 and 4.

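### The missing-data sensitivity models in SAP 5.3.2 omit the group-by-visit term, so they force one group effect on every visit and cannot serve as a reliable MAR check

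*SAP*

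**What the plan says.** The primary immunogenicity analyses use observed results without imputation. SAP 5.3.2 adds an optional sensitivity analysis if 10% or more of any group lack hSBA data for reasons other than withdrawal. For titers it is a mixed model for repeated measures fitted by maximum likelihood under MAR, with an unstructured covariance and a random intercept. Its terms are printed as "Log (hSBA)} = \text{randomized group(s)} + \text{race} + \text{sex} + \text{geographic location (US; ex-US)} + \text{age at randomization} + \text{visit". The output is the type III tests, and "least-squares GMTs at each visit will be summarized for each strain".

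For the binary endpoints, SAP 5.3.2 plans a logit-link GLIMMIX and gives no separate formula: "The model will be similar to above". For the 4-fold response, "the GLIMMIX will use baseline hSBA titer as covariate and blood sampling time points at Visits 2 and 4 as repeated dependent variables". Composite responses are handled like the titers, "with composite responses at all 3 visits modeled as dependent variables". The output is model-estimated response rates with 95% CIs.

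The primary ACWY comparison that these models would support crosses visits: "1 month after Vaccination 2 in Group 1 compared to 1 month after Vaccination 1 in Group 2" (SAP 6.1.1.1.1), with the same pattern for Groups 3 and 4 in SAP 6.1.1.2.1. The MenB comparison is between arms at Visit 4. Neither document adds a group-by-visit term anywhere.

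**The concern.** With main effects only, the group difference is a single number: on the log scale for titers, on the logit scale for responses. Three features of the trial make that untenable.

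- Baseline is one of the outcomes in the titer and composite models, and randomisation makes the expected group difference there zero.
- Groups 1 and 3 receive a second ACWY dose at Visit 3. Groups 2 and 4 receive only Trumenba then (Protocol 6.1.1, Table 2, and 8.10.1.3).
- The SAP itself follows the comparator arms over that interval: "hSBA GMTs for each of the MenACWY test strains, at baseline and 7 months after Vaccination 1 in Groups 2 and 4" (SAP 6.3.1.1.3).

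The least-squares GMTs requested for each visit are therefore forced parallel between arms and cannot show visit-specific differences.

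What is at stake is interpretation. If the models are run and disagree with the primary result, the gap may be read as an effect of missing data when it comes from the missing interaction. If they agree, the agreement may be accidental. In a noninferiority trial the awkward case is a MenB deficit pulled toward zero.

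**Working it through.** The documents give no numerical result for these models, so there is no figure to reproduce. The checks below ask what the printed models return with **complete data**, at 2:1 allocation. Race, sex, region and age were left out.

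**1. Does additivity fit the Phase 2 figures?**

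Inputs for naïve MenC: comparator rate 70% after one dose (Protocol Table 7). The difference after one dose is "5.5% (-1.3, 11.9) for serogroup C" (Protocol 2.2.2.3). The difference for two MenABCWY doses against one comparator dose is +26.5 points (same section). So MenABCWY is 70 + 5.5 = 75.5% at Visit 2 and 70 + 26.5 = 96.5% at Visit 4, a gain of 21 points.

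A constant logit difference requires

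logit p(comparator, V4) = logit p(comparator, V2) + logit p(MenABCWY, V4) − logit p(MenABCWY, V2)

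= logit(0.70) + logit(0.965) − logit(0.755) = 0.847 + 3.317 − 1.126 = 3.038, i.e. about 95.4%.

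The comparator would have to rise from 70% to about 95% with no second ACWY dose. The same step gives 94.8% for MenW (from 75.9%, with Phase 2 differences 10.7 and 21.5) and 88.4% for MenY (from 71.9%, with 14.1 and 22.9).

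**2. Logistic model, 4-fold ACWY response.**

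The comparator rate at Visit 4 is not in the documents; 30% to 70% is assumed. Fitting logit p = intercept + group + visit to the naïve MenC rates gives:

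| Quantity | True | Fitted, comparator V4 = 30% | Fitted, comparator V4 = 70% |
|---|---|---|---|
| MenABCWY V4 − comparator V2 | +26.5 | 86.2 − 49.5 = +36.8* | 91.6 − 60.1 = +31.4* |
| Difference at V2 | +5.5 | 85.8 − 49.5 = +36.3 | 80.4 − 60.1 = +20.3 |
| Comparator rate at V2 | 70% | 49.5% | 60.1% |

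*Differences taken before rounding.

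A fuller version, with a random intercept (SD 0.7 to 1.5) and baseline titer as covariate, moves these by less than 0.5 point: the contrast is +36.8 to +31.2. For naïve MenW the simple fit gives +29.1 to +24.5 (true +21.5), and for MenY +29.8 to +25.3 (true +22.9), with comparator Visit 4 from 30% up to its Visit 2 rate.

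For experienced MenY, take the 94.6% in Protocol Table 8 as the comparator rate and assume Group 4 falls to between 90% and 80% at Visit 4. The fitted contrast is −1.1 to +0.1 points, against a true −1.6.

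**3. Logistic models, MenB, true Visit 4 difference −10 points.**

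Visit 4 reference rates come from Protocol Table 9 (A22 73.8%, B24 64.5%). The comparator Visit 2 rate is assumed at 30% to 50%.

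| Assumed Visit 2 difference | Fitted Visit 4 difference (4-fold) |
|---|---|
| +5 | about −2.5 |
| 0 | about −5 |
| −10 | −9.4 to −11.1 |
| −15 | −11.8 to −14.4 |

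For the composite (Visit 4 reference 72.9%; assumed baseline rate 1% to 3%, comparator Visit 2 rate 15% to 30%, Visit 2 difference +5 to −10), a true −10 is fitted as −2.3 to −13.5.

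**4. Titer model.**

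With covariance matrix S across the three visits, the common group effect is a weighted mean of the visit-specific differences, with weights w = S⁻¹1 / (1′S⁻¹1). Equal variances and equal correlations give w = (1/3, 1/3, 1/3). A GMT ratio of 0.67 present only at Visit 4 then becomes 0.67^(1/3) = 0.875; present at Visits 2 and 4, it becomes 0.67^(2/3) = 0.77.

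With baseline log-SD 0.8, post-dose log-SD 1.2 and correlation 0.6, w = (0.90, 0.05, 0.05), and a Visit 4-only ratio becomes 0.67^0.05 = 0.98.

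Over correlations 0.2 to 0.6 and Visit 2 ratios of 1.0, 0.82 or 0.67, the fitted ratio is 0.77 to 0.98 for baseline log-SD 0.8 to 1.2, and 0.91 to 1.05 for 0.6. The same ratio is imposed at baseline, where the truth is 1.

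**5. With the interaction added**, the true values were recovered in every scenario where that model was fitted, including titer simulations with 10% of values missing at random positions.

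**The case against.** **No decision depends on these models.** They run only if the 10% trigger is met, and even then at the sponsor's option. Noninferiority rests on the Miettinen-Nurminen intervals, and an mITT analysis is also planned (conditional for MenB). This stands, and it limits the finding to the value of the sensitivity analysis.

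**GMTs are exploratory, and the SAP names no between-arm GMT ratio as output.** This also stands. What remains for the titer model is that its visit-specific GMTs are forced parallel.

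**The GLIMMIX terms are inferred, and programming rules are kept in separate documents.** That is correct, but the only reference given is the printed titer formula, and nothing in the text points to a different mean structure.

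**The Phase 2 evidence is selective.** In five of the eight serogroup-by-stratum cells (naïve MenA and all four experienced cells) the two reported differences move by 1.5 points or less. Even in naïve MenC the second figure compares different visits, so a formal test of additivity needs a comparator Visit 4 rate that is not given. This is fair: the Phase 2 support is strong for naïve C, W and Y only. Elsewhere a misfit depends on assumed waning, and the experienced MenY error is small, 0.5 to 1.7 points.

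**The MenB sizes follow from assumed Visit 2 values, and with no difference at either visit the model returns zero.** This is true. They show that the result can move in either direction, not which way it will move.

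**Conclusion.** The concern holds. As printed, the titer model cannot represent visit-specific group differences, and the logistic models inherit that on their natural reading. The structural conclusion needs only the formula, randomisation and the dosing schedule.

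The size depends on inputs that the documents lack: comparator Visit 4 rates for ACWY, Visit 2 rates for MenB, and titer SDs and correlations. Over the ranges assumed, the error in the naïve MenC contrast is about +5 to +10 points, enlarging an already favourable difference. For a true MenB deficit of 10 points, the 4-fold error runs from about 7.5 points toward zero to about 4.4 points away from it.

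The primary conclusion is not threatened. The MAR check is unreliable and should be corrected before it is used. Confidence is high for the titer model and somewhat lower for the GLIMMIX, whose terms are not listed.

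**What to change.** In SAP 5.3.2:

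- Add group-by-visit to the titer model and to both logistic models. The 4-fold model already has baseline titer as a covariate, so this is its only structural change.
- In the titer and composite models, move baseline to the covariates or constrain it to be equal across arms.
- Name the contrasts that match the primary estimands: Group 1 at Visit 4 minus Group 2 at Visit 2; Group 3 at Visit 4 minus Group 4 at Visit 2; and Groups 1+3 minus Groups 2+4 at Visit 4. Report them as risk differences with 95% CIs for the binary endpoints.
- As a separate tidy-up, drop the random intercept from the titer model, where it is redundant with an unstructured covariance.

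The cost is SAP wording and a few more parameters; no new data are needed. The change should be made before unblinding, since adding the term later would be post hoc.
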